2. STATISTICAL HYPOTHESES

The co-primary hypotheses of this study are that guselkumab is superior to placebo in inducing:

- clinical remission (CDAI score <150) at Week 12; and
- endoscopic response (\geq 50% improvement from baseline in the SES-CD score) at Week 12

The secondary hypotheses of the study are that guselkumab is superior to placebo in achieving:

- clinical remission at Week 24
- PRO-2 remission at Week 12 (defined as an AP mean daily score at or below 1 and stool frequency (SF) mean daily score at or below 3, ie, AP ≤1 and SF ≤3, and no worsening of AP or SF from baseline)
- clinical response (decrease from baseline in CDAI ≥100 points or clinical remission) at Week 12

The co-primary endpoints and secondary endpoints will be analyzed based on the estimands defined in sections 5.3.2.1 and 5.4.2.1, considering treatment groups, population, variable (endpoint), intercurrent event (ICE) strategies, and population-level summary.

Statistical testing will be performed at a significance level of 0.05 (2-sided). The Type I error rate will be controlled over the co-primary endpoints, secondary endpoints, and two Week 48 exploratory endpoints (clinical remission at Week 48, endoscopic response at Week 48). See more details in Section 5. Note the exploratory endpoints are referred to as tertiary endpoints in the protocol.

The study will be considered successful if the tests for both co-primary endpoints are positive.

The co-primary and secondary endpoints (as well as all endpoints through Week 24) will be evaluated at the Week 24 DBL. The evaluation of the Week 48 endpoints, including the Week 48 exploratory endpoints that are included in the testing procedure, will be evaluated at the subsequent Week 48 DBL.

3. SAMPLE SIZE DETERMINATION

Clinical Remission at Week 12

Assumptions for clinical remission at Week 12 were based on the Phase 2 data from the CNTO1959CRD3001 Phase 2/3 program. In the Phase 2 study (GALAXI 1), the proportions of participants who met the eligibility requirement for the GRAVITI study and who were in clinical remission at Week 12, were 12.0%, 59.2%, 55.6% and 42.9% for placebo, guselkumab ^{CCI}, guselkumab ^{CCI}, guselkumab ^{CCI}, guselkumab ^{CCI}, respectively, for a treatment difference of approximately 31% to 47%. Of note, in GALAXI 1, approximately 50% of the participants were BIO-Failure.

Note that the eligibility criterion on SES-CD for this study is relatively new and not many historical studies have this requirement, hence the actual placebo rate could vary. Based on these considerations and the data above, the clinical remission rates at Week 12 are assumed to be 15% for placebo and 50% for guselkumab ^{CCI} (treatment difference of 35%), assuming about 50% of the participants will be BIO-Failure in this study.

Endoscopic Response at Week 12

Assumptions for endoscopic response at Week 12 were also based on GALAXI 1. The proportions of participants who met the eligibility requirement for this current study and who were in

endoscopic response at Week 12, were 12.0%, 34.7%, 35.6% and 22.4% for placebo, guselkumab CCL guselkumab CCL and guselkumab CCL respectively, for a treatment difference of approximately 10% to 24%.

Based on these data, the endoscopic response rates are assumed to be 13% for placebo and 30% for guselkumab ^{CCI} (treatment difference of 17%), assuming about 50% of the participants will be BIO-Failure in this study.

In the GRAVITI study, 212 participants in the combined guselkumab group and 106 participants in the placebo group will provide at least 90% power for achieving the co-primary endpoints of clinical remission at Week 12 and endoscopic response at Week 12 (Table 1), based on the assumptions above.

Table 1:	Power to Detect a Treatment Effect of Guselkumab Based on Proportion of Participants
	Achieving Clinical Remission at Week 12 or Endoscopic Response at Week 12

Co-primary Endpoint of Clinical Remission at Week 12					
Placebo	Guselkumab SC	Power			
(N=106)	(N=212)				
15%	45%	>99%			
15%	50%	>99%			
15%	55%	>99%			
Co-prim	ary Endpoint of Endoscopic Response at	Week 12			
10%	25%	91%			
13%	30%	94%			
13%	35%	>99%			
Abbraviations: SC-subautanaous					

Abbreviations: SC=subcutaneous

4. ANALYSIS SETS

For purposes of analysis, the following analysis sets are defined:

Population	Description
Randomized Analysis Set	All randomized participants
Full Analysis Set	All randomized participants who received at least 1 dose of study
	intervention
Safety Analysis Set	All randomized participants who received at least 1 dose of study
	intervention
PK Analysis Set	All randomized participants who received at least 1 dose of study
	intervention and have at least 1 valid blood sample available post
	baseline for PK analysis
Immunogenicity Analysis Set	All randomized participants who received at least 1 dose of study
	intervention and have appropriate samples for anti-drug antibody
	detection

Note that the 3 randomized subjects at site W30-PL10064 were excluded from all analysis sets because the subject identifications could not be verified, the source data could not be verified, and study intervention administration could not be confirmed.

Unless otherwise specified, all efficacy analyses will be based on the Full Analysis Set, all safety analyses will be based on the Safety Analysis Set, all PK analyses will be based on the PK Analysis Set, and all immunogenicity analyses will be based on the Immunogenicity Analysis Set.

Efficacy data will be analyzed according to randomized treatment group. In general, safety data will also be summarized according to their assigned treatment. However, participants assigned to placebo who incorrectly received guselkumab at any time will have their safety data analyzed in the guselkumab group from the time they received guselkumab.

5. STATISTICAL ANALYSES

5.1. General Considerations

Statistical testing will be performed at a significance level of 0.05 (2-sided). The Type I error rate will be controlled over the co-primary endpoints, secondary endpoints, and two Week 48 exploratory endpoints (clinical remission at Week 48, endoscopic response at Week 48). For endpoints that are not multiplicity-controlled, nominal p-values will be presented.

- Unless otherwise specified, data from all investigational centers/sites will be pooled for analysis.
- Study Day 1 refers to the day of the first study intervention administration. All efficacy and safety assessments at all visits will be assigned a day relative to this day.

Study day for a visit is defined as:

- Visit date (date of Study Day 1) +1, if visit date is \geq date of Study Day 1
- Visit date date of Study Day 1, if visit date < date of Study Day 1

There is no 'Study Day 0'.

• Baseline is defined as the last observation prior to or on the day of the first study intervention, unless otherwise specified.

5.1.1. Visit Windows

Unless otherwise specified, nominal scheduled visits (described in SoA of the protocol) will be used for over time summaries and listings with no visit windows applied. However, the Unscheduled Visit (USV), Study Intervention Discontinuation (SID) and Final Efficacy and Safety (FES) visits will be slotted to scheduled visits according to the following mapping rules except for SES-CD endpoint:

- 1. Assign a visit number to USV, SID or FES visit based on the Study Day as illustrated in Table 2
- 2. If USV, SID or FES visit falls in the window of a scheduled visit and there are not already data for the scheduled visit, assign the scheduled visit number to the USV, SID or FES visit. If there are already data for a same scheduled visit, those data will be used in lieu of the USV, SID or FES visit data.

Week 4	Day 2-42
Week 8	Day 43-70
Week 12	Day 71-98
Week 16	Day 99-126
Week 20	Day 127-154
Week 24	Day 155-182
Week 28	Day 183-210
Week 32	Day 211-238
Week 36	Day 239-266
Week 40	Day 267-294
Week 44	Day 295-322
Week 48	Day 323-350
Week 52	Day 351-378
etc.	
Week 96	Day 659-686

Table 2: SID/FES/Unscheduled Visit Slotting

More frequent measurements are taken for other endpoints compared to endoscopic assessments taken only at Weeks 0, 12, 48, and 96.

For SES-CD endpoint using a wider window: +/- 4 weeks

Week 12: Days 57 to 113

Week 48: Days 309 to 365

Week 96: Days 645 to 701

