5.5.1.5. Histologic assessment

Histologic assessment will be performed using biopsy samples collected during endoscopy. Two biopsy samples from each of the 5 segments will be collected at screening, Week 12, Week 48, and Week 96 from each of 5 predefined anatomic locations: ileum, right colon, transverse colon, left colon, and rectum.

Biopsies will be collected from representative areas that are consistent with the mucosal appearance visually observed during endoscopy. In a segment with ulcers, all biopsies will be taken from the edge of the ulcer. In a segment without ulcers but with macroscopically abnormal areas, biopsies will be taken from the most inflamed area. In a segment that is endoscopically normal, random biopsies will be taken.

Histologic assessment will be conducted by a group of central expert pathologist readers who are blinded to treatment groups, sites and visits. The modified Global Histology Activity Score (GHAS), Geboes grading scale and Robarts Histologic Index (RHI) will be used to evaluate histologic improvement.

Modified Global Histology Activity Score

The Global Histology Activity Score was first described in 1998, and has been subsequently utilized in a number of studies resulting in peer-reviewed publications (D'Haens et al 1998; D'Haens et al 1999; Mojtahed et al 2014; Baert et al 1999; Laharie et al 2011; Mantzaris et al 2009).

All biopsies for each region will be scored in a blinded manner using the GHAS, with minor adaptations for the circumstances of this study:

- At each time point, all biopsies (up to 2 biopsies per region) obtained from each of the predefined anatomic regions will be scored separately for each of the 8 histological features; feature 8 has been modified from the original GHAS:
 - 1. epithelial damage (scored 0-2)
 - 2. architectural changes (scored 0-2)
 - 3. infiltration of mononuclear cells into the lamina propria (scored 0-2)
 - 4. polymorphonuclear cells in the lamina propria (scored 0-2)
 - 5. polymorphonuclear cells in the epithelium (scored 0-3)
 - 6. the presence of erosions/ulcers (1 for presence and 0 for absence)
 - 7. presence of granulomas (1 for presence and 0 for absence)

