The estimates of the treatment difference between the combined guselkumab group or each guselkumab group versus the placebo group will be provided by the difference in the least squares means (LSmeans). The 95% confidence interval (CI) for the differences in LSmeans and p-values will be calculated based on the MMRM. An unstructured covariance matrix for repeated measure within a subject will be used. The F-test will use Kenward-Roger's approximation for degrees of freedom. In case of lack of convergence, empirical structured covariances will be used in the following order until convergence is reached: 1) Toeplitz 2) first order Autoregressive Moving Average. If the normality assumption is in question, an appropriate transformation will be used.

Continuous endpoints involving SES-CD or histologic endpoints that are measured only at Week 12 will be compared using an analysis of covariance (ANCOVA) with treatment as a fixed factor, and baseline score, CDAI (\leq 300 or > 300), baseline SES-CD (\leq 12 or > 12), and Bio-Failure status (yes or no) as covariates. Continuous endpoints involving SES-CD will not include SES-CD strata in the model. Multiple imputation (MI) will be used for imputing missing Total SES-CD data under the assumption that the data are missing at random (MAR). For continuous endpoints involving GHAS and RHI, no imputation will be performed for missing GHAS or RHI values; the missing values will remain as missing. For binary endpoints, NRI will be used to impute missing GHAS, Geboes and RHI endpoints.

After Week 24

Two exploratory endpoints (clinical remission at Week 48, endoscopic response at Week 48) will be controlled for multiplicity. The analyses of the two endpoints will be placed after the 6 sequential tests of the co-primary and secondary endpoints in the multiple testing procedure described in Section 5.4.3.1. If all 6 p-values are <0.05, the testing procedure will continue with the 4 tests of these two endpoints (clinical remission at Week 48, endoscopic response at Week 48, for both dose groups) using the Hochberg procedure (Y Hochberg, Biometrika (1988), 75, 4, pp.800-2) with a 2-sided alpha of 0.05. The Type I error will be controlled over the co-primary, secondary, and these two Week 48 exploratory endpoints in this multiplicity-controlled testing procedure.

The testing of other exploratory endpoints will not be controlled for multiplicity, and nominal p-values will be provided.

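### The ±4-week visit window in SAP 5.1.1 covers SES-CD but not the histology taken at the same colonoscopy, so one off-schedule procedure can count for one reading and not the other

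*SAP*

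**What the plan says.** SAP 5.1.1 has three layers.

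- Data recorded under a nominal scheduled visit are taken as they stand: nominal visits "will be used for over time summaries and listings with no visit windows applied".
- Unscheduled, SID and FES visits "will be slotted to scheduled visits according to the following mapping rules except for SES-CD endpoint". SAP Table 2 then gives Week 12 as Days 71-98, Week 48 as Days 323-350 and Week 96 as Days 659-686. Data already present at the scheduled visit take precedence over slotted data.
- SES-CD has its own rule: "For SES-CD endpoint using a wider window: +/- 4 weeks", spelled out as "Week 12: Days 57 to 113", "Week 48: Days 309 to 365" and "Week 96: Days 645 to 701". The reason given is that other endpoints are measured more often than endoscopy.

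Histology is not mentioned in SAP 5.1.1, and no window for GHAS, Geboes or RHI appears elsewhere. SAP 5.5.1.5 states: "Histologic assessment will be performed using biopsy samples collected during endoscopy". Its post-baseline time points are Weeks 12, 48 and 96, the same as for SES-CD.

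On missing values, SAP 5.5.3 says: "For binary endpoints, NRI will be used to impute missing GHAS, Geboes and RHI endpoints". Continuous GHAS and RHI values are not imputed.

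**The concern.** SES-CD and histology are two readings of one procedure on one sparse schedule, so the SAP's reason for the wider SES-CD window applies equally to the biopsies. As written, the two readings follow different rules. A colonoscopy inside the SES-CD window but outside the SAP Table 2 slot supplies a valid SES-CD for the target visit, while its biopsies are assigned to a neighbouring visit at which no histologic endpoint is defined.

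At stake are the histologic endpoints in SAP 5.5.2.10. Of these, 21 are binary (seven each for GHAS, Geboes and RHI), and nine of the 21 are histo-endoscopic and need both readings. For those nine, a participant can be scored as a failure because the biopsies were slotted elsewhere, while the endoscopic half is counted from that same colonoscopy.

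**Working it through.** **1. Reproduce the SES-CD windows.** Study Day 1 is the first dose, so the target day for week w is 7w + 1, and the window is that day ± 28.

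- Week 12: 85 ± 28 = Days 57-113
- Week 48: 337 ± 28 = Days 309-365
- Week 96: 673 ± 28 = Days 645-701

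All three match the SAP.

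**2. Compare with the SAP Table 2 slots.**

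| Visit | SES-CD window | SAP Table 2 slot | Counts for SES-CD only |
|---|---|---|---|
| Week 12 | 57-113 (57 days) | 71-98 (28 days) | 57-70 and 99-113 |
| Week 48 | 309-365 (57 days) | 323-350 (28 days) | 309-322 and 351-365 |
| Week 96 | 645-701 (57 days) | 659-686 (28 days) | 645-658 and 687-701 |

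At each visit the gap is 14 early days plus 15 late days: 57 − 28 = 29 days, and 29/57 = 51%.

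**3. Can protocol-directed biopsies land in the gap?** Protocol Section 1.3, Table 5, ties colonoscopy with biopsies to particular discontinuation times.

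- A SID at Week 8 falls nominally on 7 × 8 + 1 = Day 57. That is in the SES-CD Week 12 window but in the SAP Table 2 slot for Week 8 (Days 43-70).
- If the SID comes before Week 8, the procedure moves to the FES visit, about 12 weeks after the last dose. After a Week 4 dose (Day 29) that is 29 + 84 = Day 113. SES-CD counts at Week 12; SAP Table 2 says Week 16 (Days 99-126).
- A SID at Week 44 falls on 7 × 44 + 1 = Day 309. SES-CD counts at Week 48; SAP Table 2 says Week 44 (Days 295-322).

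No histologic endpoint exists at Week 8, 16 or 44.

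**4. Remove the cases where the window makes no difference.**

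- Endoscopies recorded under the nominal visit count for both readings, whatever the day.
- Where scheduled-visit data exist, they are used.
- Discontinuation before the target visit under ICE 3 or ICE 5 is composite non-response (SAP 5.3.2.1 and 5.4.2.1, applied to exploratory binary endpoints by SAP 5.5.3). Both readings then fail regardless of window. For continuous endpoints, SAP 5.5.3 assigns baseline values after a composite ICE.

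Three routes remain, each requiring that there be no scheduled-visit data and no earlier composite ICE:

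1. An unscheduled endoscopy in a continuing participant, for example on Day 105.
2. A stop under ICE 4, which is handled by treatment policy, so that later data are used. The Day 57, Day 113 and Day 309 cases above are examples.
3. An endoscopy after the target visit, for example at a SID on Days 99-113 in a participant who had none at Week 12. Any ICE then came after the Week 12 visit.

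**5. What happens on those routes.** SES-CD from the procedure is used. Binary histologic and histo-endoscopic endpoints are set to non-response; continuous GHAS and RHI values stay missing.

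**The case against.** The strongest reply is that this is a slip of wording. The rationale in SAP 5.1.1 speaks of endoscopic assessments, which include the biopsies; only the label SES-CD endpoint is narrow. A reader might infer that the authors chose a stricter window for histology. The documents do not support that: histology is never named in SAP 5.1.1, and the narrow slot follows only from its absence from the exception. The reply stands on intent, but a programmer working from the text would still code histology to SAP Table 2.

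The second reply concerns reach, and most of it stands. Besides the exclusions in step 4 of the working, Protocol Table 5 makes SID endoscopy optional after Week 48 and before Week 96. It does not require it at a SID after Week 96, and FES endoscopy applies only when the SID preceded Week 8. So Days 351-365, 645-658 and 687-701 will hold few or no protocol-required procedures.

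A reader might also infer a head count. If 2-5% of 318 participants (6 to 16) had an off-schedule endoscopy, then 51% of them would be 3 to 8 per time point. The documents do not support this. They give no such share, and Table 5 ties procedures to particular visits rather than spreading them evenly. Non-responder imputation also changes a result only for a participant who would have responded. For histo-endoscopic response at Week 12, which requires endoscopic response, the plan's assumed rates of 30% and 13% average (212 × 0.30 + 106 × 0.13)/318 = 24%. Even on the assumed inputs, that leaves at most about 1 to 2 participants. Histologic response and remission are also restricted to participants with histologic disease at baseline, so 318 is not their base.

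**Conclusion.** The inconsistency is real on the text: 29 of 57 days at each of Weeks 12, 48 and 96 count for SES-CD but not for histology from the same colonoscopy. Its effect is confined to the three routes in the working. The number of participants affected cannot be computed from the documents and is likely small.

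It would be wrong to infer that the trial's main conclusions are touched. Co-primary endoscopic response at Week 12 and the multiplicity-controlled endoscopic response at Week 48 use SES-CD and its wider window, and the clinical endpoints do not depend on this rule. The affected endpoints are exploratory with nominal p-values, and the rule is the same in every arm. Nor is every missed biopsy a failure: that holds for binary endpoints only.

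The conclusion rests on reading the exception literally and on no histology window being set elsewhere. This is a minor correction, worth making because the stated rule discards valid biopsies for no reason the SAP gives.

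**What to change.** In SAP 5.1.1, change both the exception and the wider-window line from the SES-CD endpoint to all endpoints derived from ileocolonoscopy: SES-CD, histologic and histo-endoscopic. Both readings from one procedure then use Days 57-113, 309-365 and 645-701, and the mismatch falls from 29 days to 0 at each visit. Keep the existing precedence for scheduled-visit data.

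The cost is a few words in the SAP and one programming line. The co-primary and multiplicity-controlled analyses do not change. If Week 12 histology tables have already been produced, they would need to be rerun.
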